3.4.2 Secondary Efficacy Endpoints

Similar ANCOVA models as described for the primary analyses will be used to analyze the secondary efficacy endpoints and will be tested sequentially at the 0.05 significant level according to the order specified below:

- Percentage change from Baseline to Days 30, 180, 270 and 365 in LDL-C in the obicetrapib group compared to the placebo group;
- Percentage change from Baseline to Days 84, 180, and 365 in ApoB in the obicetrapib group compared to placebo group;
- Percentage change from Baseline to Days 84, 180, and 365 in non-HDL-C in the obicetrapib group compared to placebo group;
- Percentage change from Baseline to Days 84, 180, and 365 in HDL-C in the obicetrapib group compared to placebo group;
- Percentage change from Baseline to Days 84 in Lp(a) and ApoA1 in the obicetrapib group compared to placebo group;

- Percentage change from Baseline to Days 84, 180, and 365 in TC in the obicetrapib group compared to placebo group;
- Percentage change from Baseline to Days 84, 180, and 365 in TG in the obicetrapib group compared to placebo group.

For the percentage change from Baseline to Day 30, 180 and 270 in LDL-C, the LDL-C will be calculated using the Friedewald equation unless the Triglyceride value is ≥ 400 mg/dL or the LDL-C value is ≤ 50 mg/dL; in which case, the LDL-C level measured directly by PUC will be used in the analysis. The latter approach will be used because PUC assessments are not performed at Day 30, 180 and 270 as per the protocol, unless the conditions for Triglycerides or LDL-C described above are met at the Day 30, 180 and 270 assessments. The analysis will be repeated using the Martin-Hopkins equation as described in the [Section 3.4.1](#) above.

3.4.3 Exploratory Efficacy Endpoints

Similar ANCOVA models as described for the primary analyses will be used to assess the percentage change from Baseline to Day 365 in HbA1c, HOMA-IR and blood glucose in the obicetrapib group compared to the placebo group.

To assess the percentage change from Baseline to Day 30, 84, 180, 270 and 365 in LDL-C in the obicetrapib group compared to the placebo group in participants who were statin intolerant a similar ANCOVA model as for the primary analyses will be used. For the percentage change from Baseline to Day 84 and 365, the LDL-C will be calculated using PUC. For the percentage change from Baseline to Day 30, 84, 180, 270 and 365, analysis will be performed using the Martin-Hopkins equation as described in Section 3.4.1 above.

The proportion of participants at Days 84, 180, and 365 who achieved LDL-C < 70 mg/dL (< 1.8 mmol/L), LDL-C < 55 mg/dL (< 1.4 mmol/L), and LDL-C < 40 mg/dL (< 1.0 mmol/L) in the obicetrapib group compared to the placebo group, will be examined using logistic regression models with covariates of treatment group, Baseline LDL-C value, CV risk (HeFH or non-HeFH), and Baseline statin therapy (HIS or non-HIS). Odds ratio with 95% confidence intervals will be estimated.

The logistic regression model will be implemented using SAS® Proc LOGISTIC. The sample SAS code can be found below:

```
*****
Note:
TREATMENT = 0 (Placebo), 1 (Obicetrapib)
BASE = Baseline LDL_C value
CVRISK = 1 (HeFH), 2 (non-HeFH)
STATIN = 1 (HIS), 2 (non-HIS)
LDLC70 = LDL_C value less than 70mg/dL at DAY84 (YES/NO) for example
*****
proc logistic data= LDL_C;
  Class TREATMENT(ref=0) CVRISK STATIN / Param= Ref;
  Model LDLC70= TREATMENT BASE CVRISK STATIN / alpha=0.05 expb plcl plrl orpvalue lackfit;
  Ods output
    ParameterEstimates= Log_LDLC70_ParameterEstimates
    CLoddsPL= Log_LDLC70_OddsRatios
    ;
Run;
```

For the time from Randomization until the first confirmed occurrence of event

the following analysis will be performed. The participants who withdraw from the study before the occurrence of event or event did not occur will be censored. For these participants the time-to-event will be defined as time between Randomization and ET/EOS. Other atherosclerotic events such as AAA and carotid revascularization will be identified using the preferred terms (see [Appendix C](#)). The Clinical Events Committee (CEC) adjudicated date of event will be used to identify the first confirmed occurrence of event where appropriate, otherwise the date of event as recorded in eCRF will be used. In case when CEC cannot provide adjudicated date of death, the latest date of the last dose of study drug or date of last visit will be imputed as date of death for analysis.

The Log-rank Test

The log-rank test, stratified by CV risk (HeFH or non-HeFH), and Baseline statin therapy (HIS or non-HIS) will be used to compare differences in the time-to-event between obicetrapib and placebo.

The sample SAS code can be found below:

Note:

TREATMENT = 0 (Placebo), 1 (Obicetrapib)
CVRISK = 1 (HeFH), 2 (non-HeFH)
STATIN = 1 (HIS), 2 (non-HIS)
TIME = Time from Randomization until the first occurrence of event
CENSOR = 0 (Event occurred), 1 (Event did not occurred)

```
proc lifetest data= time_to_event method=KM  
    strata CVRISK STATIN/test=logrank group=TREATMENT;  
    time TIME*CENSOR;
```

Run;

Cox Proportional Hazard Model

A Stratified Cox proportional hazard model will be used to estimate hazard ratio between treatment groups along with the 95% confidence intervals. The model will include treatment group, CV risk (HeFH or non-HeFH), and Baseline statin therapy (HIS or non-HIS).

The Cox proportional hazard model will be implemented using SAS® Proc PHREG. The sample SAS code can be found below:

Note:

TREATMENT = 0 (Placebo), 1 (Obicetrapib)
CVRISK = 1 (HeFH), 2 (non-HeFH)
STATIN = 1 (HIS), 2 (non-HIS)
TIME = Time from Randomization until the first occurrence of event
CENSOR = 0 (Event occurred), 1 (Event did not occurred)

```
proc phreg data= time_to_event ;  
    model TIME*CENSOR=TREATMENT;  
    strata CVRISK STATIN;
```

Run;

The proportional hazard assumption will be evaluated via examination of complementary log-log (event time) versus log (time) plots. If the proportional hazard assumption raises concerns, the non-parametric Peto-Peto-Prentice test will be applied. Nominal p-values will be provided when applicable.

The number of occurrences of CV events will be analyzed using a Poisson regression model including covariates of treatment group, CV risk (HeFH or non-HeFH), and Baseline statin therapy (HIS or non-HIS). Rate ratio with 95% confidence intervals will be estimated. The model assumption for equidispersion will be tested and if this assumption is not supported, alternative analysis and models such as negative binomial or zero-inflated Poisson model will be explored.

The Poisson regression model will be implemented using SAS® Proc GENMOD. The sample SAS code can be found below:

Note:

TREATMENT = 0 (Placebo), 1 (Obicetrapib)
COUNT = Number of events
TIME = Follow up time for each participant measured in days
LOGT = log(TIME)

proc genmod data= events ;
 class TREATMENT;
 model COUNT=TREATMENT/offset=logt disp=poisson link=log;
run;

Descriptive and graphical summaries will be presented by treatment group. Adjudicated clinical events will be presented in participants listing.

Plasma obicetrapib concentrations will be summarized with descriptive statistics based on the Safety Population.

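### The sample SAS code in SAP 3.4.3 does not implement the logistic and Poisson models in its text: the event level, the strata and the direction of the rate ratio need fixing

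*SAP*

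**What the plan says.** SAP 3.4.3 (Exploratory Efficacy Endpoints) sets out two analyses, each as text followed by sample code.

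**Goal attainment.** The target is "The proportion of participants at Days 84, 180, and 365 who achieved LDL-C < 70 mg/dL", and likewise for 55 and 40 mg/dL, comparing obicetrapib with placebo by logistic regression and reporting an odds ratio with its 95% confidence interval. The variable note reads "LDLC70 = LDL_C value less than 70mg/dL at DAY84 (YES/NO) for example". The program opens with "proc logistic data= LDL_C", sets the treatment reference with "Class TREATMENT(ref=0) CVRISK STATIN / Param= Ref", and fits "Model LDLC70= TREATMENT BASE CVRISK STATIN".

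**Total events.** The text specifies a "Poisson regression model including covariates of treatment group, CV risk (HeFH or non-HeFH), and Baseline statin therapy (HIS or non-HIS" and asks for a rate ratio with its 95% confidence interval. The program has only `TREATMENT` on its CLASS statement and fits "model COUNT=TREATMENT/offset=logt disp=poisson link=log". Its variable note lists treatment, count, time and log time. It does not list CV risk or statin therapy.

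Between these two, the same section gives log-rank and Cox code. Both programs carry CV risk and statin therapy as strata.

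**The concern.** Sample code in a SAP is what a programmer is likely to start from. Where it differs from the text, either the text is not what gets run, or someone must decide later which of the two governs.

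In the logistic program the treatment reference is fixed but the event level is not. The text is about participants who reach the goal, while the code may model those who do not. In the Poisson program the adjustment stated in the text is missing, and nothing fixes which arm is the numerator of the rate ratio.

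A reversed odds ratio for LDL-C goals would probably be noticed, because the expected effect is large. A reversed rate ratio for sparse cardiovascular events, where the true direction is not known in advance, could pass unnoticed.

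**Working it through.** The documents give no sample size, event count or power for these exploratory analyses, so there is no stated figure to reproduce. The check sets text against code and then sizes the differences. Two SAS behaviours are assumed, since the documents do not state them: PROC LOGISTIC models the lowest ordered response level unless told otherwise, and PROC GENMOD takes the last CLASS level as reference.

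**1. Logistic event level.** The levels YES and NO sort as NO, YES. The code has no `event=`, `descending`, `ref=` or `order=` for the response, so NO is modelled. Treatment is referenced to placebo, so the printed value is the obicetrapib-versus-placebo odds ratio for missing the goal: OR printed = 1 / OR intended. The confidence limits are inverted and swapped.

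OR = [p1/(1 − p1)] / [p0/(1 − p0)], for assumed attainment rates on placebo (p0) and obicetrapib (p1):

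| p0 | p1 | OR, YES modelled | OR, NO modelled |
|---|---|---|---|
| 20% | 60% | 1.5/0.25 = 6.0 | 0.167 |
| 10% | 50% | 9.0 | 0.111 |
| 5% | 30% | 8.14 | 0.123 |
| 30% | 70% | 5.44 | 0.184 |

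The adjusted model was fitted to one simulated data set: 2,400 participants, 2:1 within strata, with a 30% mean LDL-C reduction and SD 15% as in the sample-size section. Assumed: 17% HeFH, 70% on high-intensity statins, baseline LDL-C about 100 mg/dL with SD 30. Attainment of <70 mg/dL was 18% versus 52%. Modelling YES gave 18.8 (13.6 to 26.0); modelling NO gave 0.053 (0.038 to 0.073). Check: 1/18.8 = 0.053.

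Number affected: 3 thresholds × 3 visits = 9 odds ratios.

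**2. Poisson covariates.**

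| | Text | Code |
|---|---|---|
| Treatment | yes | yes |
| CV risk | yes | no |
| Baseline statin therapy | yes | no |

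The effect was sized with 300 simulated trials of the same size and allocation. Assumed: 0.05 events per year, true rate ratio 0.8, stratum rate ratios 1.5 (HeFH) and 0.7 (high-intensity statin).

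| | With strata | Without strata |
|---|---|---|
| Mean rate ratio (geometric) | 0.811 | 0.811 |
| Mean SE of log rate ratio | 0.220 | 0.220 |

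The largest difference in any one trial was 0.3%.

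**3. Poisson direction.** Treatment is coded 0 = placebo, 1 = obicetrapib. With the last level as reference, the coefficient is placebo versus obicetrapib: 1/0.811 = 1.23. Using the simulated SE, the intended 95% interval is exp(−0.2095 ± 1.96 × 0.220) = 0.53 to 1.25, and the reversed one is 1/1.25 to 1/0.53, about 0.80 to 1.90. Both include 1, so neither looks wrong on sight. The Cox code enters treatment as a 0/1 variable without a CLASS statement, so its hazard ratio runs obicetrapib over placebo, the opposite way. No statement in the Poisson program exponentiates the coefficient, so it does not output the rate ratio the text asks for.

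Number affected: SAP 2.3.3 lists 19 total-event endpoints: 2 without revascularisation, 16 combinations (CV or CHD death × non-elective or all coronary revascularisation × four levels of added components), and total CV events. 2 + 2 × 2 × 4 + 1 = 19.

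**The case against.** The best defence is that the code is only a sample. The written models are right, SAP 7 places detailed programming specifications in a separate document, and SAP 5.2 and 5.3 allow comments on pre-final output before the final analysis. Descriptive summaries by arm are also planned, so an odds ratio below 1 beside higher attainment on obicetrapib would stand out. All of this stands, and it keeps the point small. It does not remove it: nothing in either document corrects the two programs.

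The inversion is also conditional. The note gives YES/NO as the meaning of the response, without a storage code, while the other categorical variables in that note are numeric. A numeric code with YES as the lower value would avoid the problem. This is accepted. Even then, the event level should be stated.

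A reader might infer that leaving out the randomisation factors biases the rate ratios. The documents do not support that: allocation is stratified on those same factors, and the simulation shows almost no change. A reader might also infer from `disp=` that the Poisson program cannot run. That spelling may be a reading error in the text copy of the SAP, so it should be checked against the source file, and nothing here depends on it.

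**Conclusion.** The point holds as a minor mismatch between text and code. Run literally, the logistic program returns reciprocals for nine goal-attainment odds ratios, provided the response is stored as YES/NO and the SAS default applies. P-values and strength of association do not change. For 19 total-event endpoints, the Poisson program omits two stated covariates, with negligible expected numerical effect. More consequentially, under default coding it contrasts placebo with obicetrapib, and it outputs no rate ratio.

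A reader might go further and conclude that the trial's reported results will be inverted, or that its main findings are in doubt. Neither follows. The documents do not show that the sample code will be run unaltered, and the affected endpoints are exploratory, without multiplicity adjustment (SAP 3.1.6). The primary and secondary analyses use other models. The simulated sizes rest on the event rate, stratum effects and attainment rates assumed above; the reciprocal relation does not.

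**What to change.** In SAP 3.4.3:

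- Logistic: write `Model LDLC70(event='YES') = TREATMENT BASE CVRISK STATIN / ...`, and say in the text that the odds ratio is for reaching the goal, obicetrapib versus placebo.
- Poisson: write `class TREATMENT(ref='0') CVRISK STATIN;` and `model COUNT = TREATMENT CVRISK STATIN / offset=logt dist=poisson link=log;`. Add a statement giving the exponentiated treatment estimate, obicetrapib versus placebo, with its 95% confidence interval. Adding the covariates alone would leave the direction unset and still output no rate ratio.
- Add CV risk and statin therapy to the Poisson variable note, and check `disp=` against the source file.

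The cost is a few lines of code and one sentence of text, with no change to data collection, sample size or the stated models. Making the change before unblinding avoids any question of choosing the model or direction afterwards.

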#### 4.3 Withdrawal Criteria

Participation of a participant in this clinical study will be discontinued for any of the following reasons:

- Withdrawal of consent; or
- Termination of the study by the Sponsor or the regulatory authority.

Study drug treatment may be discontinued either permanently or temporarily (although the participant should be encouraged to remain in the study and to follow-up for study visits) for any of the following reasons:

- Occurrence of any medical condition or circumstance that exposes the participant to substantial risk and/or does not allow the participant to adhere to the requirements of the protocol;
- Any serious AE (SAE), clinically significant AE, severe laboratory abnormality, intercurrent illness, or other medical condition which indicates to the Investigator that continued participation is not in the best interest of the participant;
- Pregnancy (permanent discontinuation of study drug);

- Requirement of prohibited concomitant medication; or
- Participant failure to comply with protocol requirements or study-related procedures.

Participants are free to withdraw consent from the study (which means permanent discontinuation of study drug and all follow-up assessments) at any time without prejudice. Note that discontinuation of study drug in and of itself is **not** considered withdrawal of consent.

An excessive rate of withdrawals (either discontinuation of study drug or study withdrawal) can render the study non-interpretable. Therefore, unnecessary withdrawal of participants should be avoided, and all efforts should be taken to motivate participants to comply with all of the study-specific procedures and to continue follow-up until the end of the study to detect the occurrence of CV events and assess vital status.

Every attempt should be made to keep participants on study drug throughout the duration of the study. Before permanently discontinuing study drug (either participant- or Investigator-initiated), an interruption should be considered. Participants who temporarily discontinue study drug for any reason should restart as soon as it is medically justified in the opinion of the Investigator. In addition, participants should not be withdrawn from the study drug or from the study after experiencing a potential CV event.

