All participants who permanently discontinue study drug should continue scheduled study visits. If the participant declines continued onsite visits but is agreeable to telephone calls, he/she will be contacted by the Investigator periodically to assess occurrence of CV events until death, documented withdrawal of participant informed consent (in writing if allowed by local regulations), or the final closure of the study.

The Investigator should show due diligence and explore all possible options to reach a participant who fails to return for a visit. In the case of participants lost to follow-up, attempts to contact the participant must be made and documented in the participant's medical records and in source documents. Per routine, in order to avoid participants lost to follow-up, the Investigator should ask the participant at the study start for the contact details of a relative or friend who can be contacted for participant contact information in case the participant cannot be reached.

Participants should not be withdrawn from follow-up unless they explicitly withdraw consent to be contacted. All efforts should therefore be made to minimize the number of participants who withdraw consent as, in general, no further information on CV events and survival status may be collected after that point. Participants who do not want regular in-person follow-up after cessation of study drug should be offered alternative methods of follow-up, including periodic telephone follow-up, contact at study closure, or assessment of health status via treating physicians or medical records. Such participants would then not be viewed as withdrawal of consent. The Investigator must explain to the participant all options for continued participation, and document which options were refused by the participant and the reason for refusal. Withdrawal of consent to all follow-up must be ascertained and documented in writing by the Investigator, who must inform the Sponsor and document the withdrawal of consent in the eCRF and medical records.

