For participants who permanently discontinue from study treatment and who decline continued study participation, an Early Termination (ET) Visit will be scheduled as soon as possible followed by an onsite EOS Visit 35 days later. The ET Visit procedures are identical to the End of Treatment (EOT) Visit procedures. If the discontinuation occurs at a specific onsite visit, this visit will become the ET Visit and EOT Visit procedures should be followed. Participants who

withdraw consent to all follow-up will be asked about the reason(s) and will be assessed for the presence of any AEs.

For participants who completely withdraw consent, life status will be obtained at study end through public record information according to local guidelines and as allowed by local regulations.

If premature withdrawal from the study occurs for any reason, the Investigator must determine the primary reason for a participant's premature withdrawal from the study and record this information in the medical records and on the eCRF.

Withdrawn participants will not be replaced.

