Refer to [Table 1 Schedule of Procedures](#) for a complete list of procedures to be completed at each study visit.

Table 1 Schedule of Procedures

Visit	Treatment Period						EOS ¹	
	V1	V2	V3	V4	V5	V6		
Study Day	-28 to -1	1	30	84	180	270	365	35 days after last dose
Window (±days)			±3	±7	±7	±7	±7	±7
Informed consent ³	X							
Assessment of eligibility	X ⁴	X ⁴						
Demographics and medical history	X							
Pregnancy test, FSH ⁵	X	X				X		X
TSH	X							
Randomization		X						
Study drug administration		X	X	X	X	X		X
Physical examination ⁶	X							X
Weight, height, and BMI	X ⁷							X
Vital signs ⁸	X	X	X	X	X	X	X	X
24-hr ABPM ⁹	X ¹⁰						X ¹¹	
12-lead ECG ¹²		X						X
Lipid profile/biomarkers (fasting) ¹³	X	X	X	X	X	X		X
Serum archive sample for future assessment of biomarkers related to dyslipidemia and/or CV risk (fasting) ^{13,14,15}		X						X
UACR, UPCR (fasting) ¹³		X						X
Aldosterone, hsCRP (fasting) ¹³	X ¹⁶	X						X
Lp(a), ApoA1(fasting) ^{13,14}	X	X		X				
Insulin for HOMA-IR (fasting) ¹³	X	X		X	X	X		X
Full serum chemistry (fasting) ^{13,14}		X			X			X
Limited serum chemistry (fasting) ^{13,14}	X		X	X		X		
Urine dipstick analysis ¹⁷	X	X						X
Hematology and coagulation (fasting) ^{13,14}	X	X			X			X
PK sample (central) ^{14,18}		X		X ²⁰	X			X
Prior/concomitant medications	X	X	X	X	X	X	X	X
Study drug dispensation		X	X	X	X	X		

Study drug return/compliance calculations			X	X	X	X	X	
CV events assessment ¹⁹	X	X	X	X	X	X	X	X
AEs assessment	X	X	X	X	X	X	X	X

1. The onsite EOS Visit will include an assessment of vital signs, concomitant medications, CV events, and AEs will be completed and documented in the participant's record.
2. For participants who permanently discontinue from study treatment and who decline continued study participation, an ET Visit will be scheduled as soon as possible followed by an onsite EOS Visit 35 days later. If the discontinuation occurs at a specific onsite visit, this visit will become the ET Visit and EOT Visit procedures should be followed. Participants who withdraw consent to all follow-up will be asked about the reason(s) and will be assessed for the presence of any AEs. For participants who completely withdraw consent, life status will be obtained at study end through public record information according to local guidelines and as allowed by local regulations.

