- The time from Randomization until the first confirmed occurrence of a composite of CHD death, non-fatal MI, non-fatal stroke, hospitalization of unstable angina, MALE, or non-elective coronary revascularization;
- The time from Randomization until the first confirmed occurrence of a composite of CHD death, non-fatal MI, non-fatal stroke, hospitalization of unstable angina, MALE, or coronary revascularization;
- The time from Randomization until the first confirmed occurrence of a composite of CV death, non-fatal MI, non-fatal stroke, hospitalization of unstable angina, MALE, other atherosclerotic events (AAA, TIA, carotid revascularization), or non-elective coronary revascularization;
- The time from Randomization until the first confirmed occurrence of a composite of CV death, non-fatal MI, non-fatal stroke, hospitalization of unstable angina, MALE, other atherosclerotic events (AAA, TIA, carotid revascularization), or coronary revascularization;
- The time from Randomization until the first confirmed occurrence of a composite of CHD death, non-fatal MI, non-fatal stroke, hospitalization of unstable angina, MALE, other atherosclerotic events (AAA, TIA, carotid revascularization), or non-elective coronary revascularization;

- The time from Randomization until the first confirmed occurrence of a composite of CHD death, non-fatal MI, non-fatal stroke, hospitalization of unstable angina, MALE, other atherosclerotic events (AAA, TIA, carotid revascularization), or coronary revascularization;
- The time from Randomization until the first confirmed occurrence of a composite of CV death, non-fatal MI, or non-fatal stroke;
- The time from Randomization until the first confirmed occurrence of a composite of CHD death, non-fatal MI, or non-fatal stroke;
- The time from Randomization until the confirmed occurrence of CV death;
- The time from Randomization until the confirmed occurrence of non-fatal MI;
- The time from Randomization until the confirmed occurrence of non-fatal stroke;
- The time from Randomization until the confirmed occurrence of non-elective coronary revascularization ;
- The time from Randomization until the confirmed occurrence of all cause death;
- The number of total events: CV death, non-fatal MI, non-fatal stroke;
- The number of total events: CHD death, non-fatal MI, non-fatal stroke;
- The number of total events: CV death, non-fatal MI, non-fatal stroke, or non-elective coronary revascularization;

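### The SAP's single ET/EOS censoring rule also governs all-cause death, so read literally it omits deaths found by the planned public-record check after consent withdrawal

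*SAP*

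**What the plan says.** SAP 2.3.3 lists among the exploratory endpoints "The time from Randomization until the confirmed occurrence of all cause death". SAP 3.4.3 then sets the censoring rule for the time-to-event endpoints as a group: "The participants who withdraw from the study before the occurrence of event or event did not occur will be censored". The censoring time follows: "For these participants the time-to-event will be defined as time between Randomization and ET/EOS". No endpoint is exempted.

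The same paragraph of SAP 3.4.3 says how a death is dated when the Clinical Events Committee (CEC) cannot supply an adjudicated date: the later of last dose and last visit is used.

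On collection, Protocol 4.3 says: "For participants who completely withdraw consent, life status will be obtained at study end through public record information according to local guidelines". Footnote 2 of the Protocol's schedule of procedures (Appendix A) and footnote 2 of SAP Table 1 repeat this. The SAP footnote reads: "life status will be obtained at study end through public record information according to local guidelines and as allowed by local regulations". Protocol 4.3 also asks sites to motivate participants to "continue follow-up until the end of the study to detect the occurrence of CV events and assess vital status", but warns that after consent is withdrawn, "in general, no further information on CV events and survival status may be collected after that point".

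No SAP sentence says how the public-record life status enters the mortality analysis.

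**The concern.** The trial plans to learn whether fully withdrawn participants are alive at study end, and its analysis rule then ends their follow-up at ET/EOS. Someone who withdraws and later dies has withdrawn before the event, so the rule censors that person and the death does not appear in the all-cause mortality comparison.

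Efficacy is analysed on all randomized participants (SAP 3.4), and a mortality analysis on that population should use every death the trial is entitled to know about. Withdrawal can be related to health. If that relation differs between arms, censoring at withdrawal is informative and the hazard ratio is biased. Even without bias, a mortality table that omits deaths held in the trial's own records is hard to defend when there are few deaths.

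**Working it through.** **Plan's own figure.** There is none to reproduce. The documents give no death rate, event count or power for all-cause death.

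**Following one participant through the text**

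1. The participant withdraws consent completely, then dies before study end.
2. Under Protocol 4.3, the public-record check at study end can reveal the death, if local regulations allow the check.
3. Under the SAP 3.4.3 censoring sentence, the participant withdrew before the event, so the record is censored at ET/EOS.
4. The date-imputation sentence in SAP 3.4.3 supplies a date for a death that lacks one. It does not say that a death after withdrawal is an event. If it were applied here, it would place the death at the last dose or last visit, close to the withdrawal date. One sentence would then censor the participant and another would count a death at about the same time. Two programmers could produce different death counts.

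**Scale (illustration only)**

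Inputs from the documents:
- N = 2400.
- EOS is 35 days after a last dose at Day 365, so 365 + 35 = Day 400 and T = 400/365.25 = 1.095 years.
- The 5% drop-out allowance in the sample-size section gives 0.05 × 2400 = 120. It is borrowed only to set a scale.

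Assumptions not in the documents:
- mortality m of 1% to 4% per year;
- withdrawn fraction w of 2% to 10%;
- withdrawals spread evenly to Day 400, so T/2 (200 days) is unobserved on average;
- mortality ratio after withdrawal, RR, of 1 or 3;
- all such deaths to Day 400 could be found in records.

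Formulas:
- omitted = N·w·m·RR·(T/2)
- counted = N·(1 − w)·m·T + N·w·m·(T/2)
- share = omitted / (omitted + counted)

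Example with w = 5%, m = 1%, RR = 1: omitted = 120 × 0.01 × 0.548 = 0.66; counted = 2280 × 0.01 × 1.095 + 0.66 = 25.6; share = 0.66/26.3 = 2.5%.

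| w | RR | Omitted (m = 1% to 4%) | Counted (m = 1% to 4%) | Share omitted |
|---|---|---|---|---|
| 2% | 1 | 0.26 to 1.05 | 26.0 to 104.1 | 1.0% |
| 2% | 3 | 0.79 to 3.15 | 26.0 to 104.1 | 2.9% |
| 5% | 1 | 0.66 to 2.63 | 25.6 to 102.5 | 2.5% |
| 5% | 3 | 1.97 to 7.89 | 25.6 to 102.5 | 7.1% |
| 10% | 1 | 1.31 to 5.26 | 25.0 to 99.9 | 5.0% |
| 10% | 3 | 3.94 to 15.77 | 25.0 to 99.9 | 13.6% |

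Under each row's assumptions these are upper figures for deaths to Day 400, because records will not be obtainable everywhere.

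**The case against.** Four points can be made for the plan.

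- **Few participants are affected.** Stopping study drug is not withdrawal of consent under Protocol 4.3, and participants who accept telephone, physician or medical-record follow-up are not withdrawals either. The public-record check covers only complete withdrawal of consent, only where permitted, and Protocol 4.3 itself expects little survival information after that point. This stands. A reader might infer that the 5% allowance means about 120 participants with known vital status who lose follow-up. The documents do not support that. The 5% is the allowance for participants not evaluable for LDL-C efficacy, and the number with a usable public record is not stated.
- **The imputation sentence may already cover these deaths.** It foresees deaths without a usable date, and the CEC adjudicates all deaths, so a public-record death might reach the analysis by that route. This stands in part: the sentence leaves some room to count such deaths. But it gives a date and does not override the censoring rule.
- **The endpoint is exploratory.** It is one of many, with nominal p-values and no multiplicity control. This stands and limits the weight of the point.
- **Using the records carelessly adds a new problem.** Life status is obtained at study end, which Protocol 10.3 ties to the last participant's last visit. Completers are censored at EOS, about Day 400. Without a common cut-off, early enrollees who withdrew would be followed longer than completers, and the late risk set would consist of withdrawn participants in countries that permit record access. This stands, and the fix has to deal with it.

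**Conclusion.** The point holds as a defect in a stated rule for one exploratory endpoint. Followed literally, SAP 3.4.3 does not count deaths that the protocol and the SAP's own schedule plan to learn about, and nothing else in the SAP clearly reverses this.

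The effect is probably small: 1% to 14% of deaths across the assumed range, with 2.5% at 5% withdrawal and no excess risk after withdrawal. All of these rest on assumed mortality, withdrawal timing and record access. The primary LDL-C result and the type I error control are unaffected.

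A reader might go further and conclude that the mortality comparison is biased. The documents do not show that. It would require withdrawal to be related to the risk of death in a way that differs by arm, and they offer no evidence either way.

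**What to change.** Give all-cause death its own rule in SAP 3.4.3, settled before unblinding so that no one decides which deaths count with the results in view:

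- Count deaths from any permitted source, including public records, as events up to one cut-off. Apply it to both arms and to completers and withdrawn participants alike, for example the planned EOS at about Day 400.
- Otherwise censor at the earlier of that cut-off and the last date known alive, including the public-record check.
- State how undated public-record deaths are dated, and reconcile this with the existing last-dose or last-visit imputation.
- State how public-record deaths without an adjudicated cause enter CV death, CHD death and the composites that contain them.
- Keep ET/EOS censoring for non-fatal events.

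The cost is a few SAP sentences, and the life-status check is already planned. The limits are that record access varies by country, and that the protocol promises life status but not a date of death, a date last known alive, or a cause. The report should therefore give, by arm, how many withdrawn participants had life status obtained.
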